## 11. SAP REVISION

Revision Date (DD MMM YYYY)	Section	Summary of Revision	Reason for Revision

## 12. APPENDIX

### Appendix 1. Health Assessment Questionnaire Disability Index (HAQ-DI)

The HAQ-DI score is defined as the average of the scores of eight functional categories (dressing and grooming, arising, eating, walking, hygiene, reach, grip, and other activities), usually administered by the patient. Responses in each functional category are collected as 0 (without any difficulty) to 3 (unable to do a task in that area), with or without aids or devices.

The highest score for questions in each category (range 0 to 3) determines the score for the category, unless aids or devices are required. Dependence on equipment or physical assistance increases a lower score (i.e., scores of 0 or 1) to the level of 2 to more accurately represent underlying disability. The eight category scores are averaged into an overall HAQ-DI score on a scale from 0 (no disability) to 3 (completely disabled) when 6 or more categories are non-missing. If more than 2 categories are missing, the HAQ-DI score is set to missing. The HAQ-DI can be treated as a continuous measure.

The HAQ-DI score using aids (and/or devices) is computed by taking the maximum score of the questions in each category (range: [0, 3]) and whether or not aids/devices are used (0 or 1):

$$\begin{aligned} A = & \max(\text{dressing \& grooming category questions}, 2*\text{aids indicator}) + \\ & \max(\text{rising category questions}, 2*\text{aids indicator}) + \\ & \max(\text{eating category questions}, 2*\text{aids indicator}) + \\ & \max(\text{walking category questions}, 2*\text{aids indicator}) + \\ & \max(\text{hygiene category questions}, 2*\text{aids indicator}) + \\ & \max(\text{reach category questions}, 2*\text{aids indicator}) + \\ & \max(\text{grip category questions}, 2*\text{aids indicator}) + \\ & \max(\text{usual activities category questions}, 2*\text{aids indicator}) \end{aligned}$$

$$\text{HAQ-DI} = A / (\text{total number of categories with at least 6 non-missing})$$

The following table shows the contribution of the 43 questions used to calculate the HAQ-DI:

HAQ-DI Category:	Category questions: At least 6 categories must have scores to compute the HAQ-DI.		HAQ-DI Category Score with Aids/Devices Calculation:
	Category Questions	Aids/Devices Indicators	
Dressing / Grooming	HAQ0101, HAQ0102 (DRESS, HAIR)	HAQ0114, HAQ0119 (DRSG, GROOM)	
Arising	HAQ0103, HAQ0104 (STAND, BED)	HAQ0116, HAQ0120 (CHAIR, ARISING)	
Eating	HAQ0105, HAQ0106, HAQ0107 (MEAT, LIFT, MILK)	HAQ0115, HAQ0121 (UTENSIL, EAT)	Using each question with a scale of 0-3, calculate the category score as the maximum of the category questions.
Walking	HAQ0108, HAQ0109 (WALK, STEPS)	HAQ0110, HAQ0111, HAQ0112, HAQ0113, HAQ0122 (CANE, WALKER, CRUTCH, WHEEL, WALKING)	If the Aids/Devices indicator is “No”, no need to adjust the category score. If the Aids/Devices indicator is “Yes” and the category score is <2, then the category score with the Aids/Devices is set to 2. If the Aids/Devices indicator is “Yes” and the category score is ≥2, then the category score with Aids/Devices is the calculated category score without adjustment.
Hygiene	HAQ0123, HAQ0124, HAQ0125 (WASH, BATH, TOILET)	HAQ0134, HAQ0135, HAQ0137, HAQ0139, HAQ0142 (RAISEAT, BATHBAR, BATHSEAT, LONGBATH, HYGIENE)	For example: The Dressing/Grooming category score is 2 if subject answered 1 for both questions 1 and 2 and “Yes” for both question 14 and 18. In the HAQ-DI score calculation, questions on other device/aids will not be used.
Reach	HAQ0126, HAQ0127 (REACH, BEND)	HAQ0138, HAQ0143 (LONGRCH, REACH)	
Grip	HAQ0128, HAQ0129, HAQ0130 (OPENCAR, JAR, FAUCET)	HAQ0136, HAQ0144 (JAROPEN, GRIP)	
Activity	HAQ0131, HAQ0132, HAQ0133 (SHOP, INCAR, CHORES)	HAQ0145 (ERRAND)	

**Handling Missing Data:** If no more than 2 categories have missing category scores, then the HAQ-DI is the mean of the non-missing category scores. Otherwise, the HAQ-DI score is set to missing.

If any of the category questions are missing, but the aids/device indicator is non-missing, the category score can still be computed. However, if all category questions and its aids/device indicators are missing, then the category score is considered missing.

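### Read literally, the HAQ-DI missing-data rule in SAP Appendix 1 scores a wholly unanswered category as 0 (no disability) when the aids indicator is No, and can bypass the limit of two missing categories

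*SAP*

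**What the plan says.** SAP Appendix 1 defines a category score as max(category questions, 2 × aids indicator), with the indicator coded 0 or 1. HAQ-DI is the average over categories, reported "on a scale from 0 (no disability) to 3 (completely disabled) when 6 or more categories are non-missing".

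Three statements govern missing data:

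- Category level, when a score exists: "If any of the category questions are missing, but the aids/device indicator is non-missing, the category score can still be computed".
- Category level, when it does not: "if all category questions and its aids/device indicators are missing, then the category score is considered missing".
- Total score: "If no more than 2 categories have missing category scores, then the HAQ-DI is the mean of the non-missing category scores". The converse is stated earlier in the appendix: "If more than 2 categories are missing, the HAQ-DI score is set to missing".

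The last column of the appendix table describes the category score in two steps. The score is the maximum of the answered questions, and it is raised to 2 if an aid is reported and the maximum is below 2. If the indicator is No, there is "no need to adjust the category score". The column does not say what happens when no question was answered.

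HAQ-DI is listed among the baseline characteristics (SAP Section 5.2) and defined under the exploratory efficacy endpoints (SAP Section 6.4.1.2).

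**The concern.** The missing-category sentence requires two things together: all questions blank and all aids indicators blank. A category with no answered question but a recorded No falls outside it and inside the sentence that allows a score. The only term left in the formula is then 2 × 0.

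Two consequences follow. First, a category about which the subject reported no difficulty level at all receives the value that means no disability. Second, that category counts as non-missing, so the completeness rule (at least six of eight categories scored) may not act on the forms it was written for.

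**Working it through.** **Inputs, all from SAP Appendix 1.** Category score = max(answered questions, 2 × aids indicator), indicator 1 for Yes and 0 for No. A category is missing only if all its questions and all its aids indicators are missing. HAQ-DI = mean of the non-missing categories if at least six of eight are non-missing, otherwise missing.

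**The plan's own example.** Both Dressing/Grooming questions answered 1 and both aids indicators Yes: max(1, 1, 2 × 1) = 2. This agrees with the 2 given in the appendix.

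**A category with no answered question.**

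- Indicator No: the only term is 2 × 0 = 0. The category is scored 0 and counts as non-missing.
- Indicator Yes: 2 × 1 = 2. This cannot be too high under the SAP's scoring, because any category with an aid reported scores 2 or 3.
- Indicator also blank: missing, as the appendix says.

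The problem is therefore confined to the first case. Since 0 is the floor of the scale, the value there can never exceed the true category score and is too low whenever that score is above 0.

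**Effect on the total (assumed scenarios).** Let every answered category score s, with m categories unanswered and their indicators No. The literal rule gives s × (8 − m)/8. If those m categories were treated as missing, the mean would be s for m ≤ 2 and HAQ-DI would be missing for m ≥ 3. With s = 2:

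| Unanswered categories (m) | Literal rule | Unanswered treated as missing |
|---|---|---|
| 1 | 14/8 = 1.75 | 14/7 = 2.00 |
| 2 | 12/8 = 1.50 | 12/6 = 2.00 |
| 3 | 10/8 = 1.25 | missing |
| 8 | 0/8 = 0.00 | missing |

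The relative shortfall is m/8: 12.5% at m = 1 and 25% at m = 2, whatever the value of s. From m = 3 the literal rule still returns a score although more than two categories have no answers.

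**Effect on a group mean.** SAP Section 1.3 gives 15 subjects enrolled, and allocation was planned as 1:1:1. The documents do not give the actual split. Assuming 5 per group, one subject with a 0.50 shortfall moves the group mean by 0.50/5 = 0.10.

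**The two parts of the appendix side by side.** The missing-data text with the formula gives 0. The table column takes the maximum of the questions before looking at the indicator, and No leaves that result as it is. With nothing answered there is no maximum, so the column leads to a missing category. The same form can be derived in two ways.

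**The case against.** The strongest reply is that the SAP nowhere writes that such a category scores 0. The value is derived by combining the formula with the missing-data sentences. A programmer following the table column would have no score to start from and would leave the category missing. The sentence allowing a score has two harmless uses: some questions answered, or none answered but an aid reported. SAP Section 3.6.1 also leaves missing data unimputed unless a method is specified, and no sentence expressly substitutes 0. On that reading the six-category minimum works as intended.

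Much of this stands. A reader might infer that the plan openly imputes no disability for unanswered categories; it does not, and the 0 is a consequence of literal evaluation. The reply does not remove the problem, however. The only sentence that makes a category missing requires the indicators to be blank as well, and the sentence before it says a score can be computed when the indicator is present. The reading that saves the rule has to set those words aside.

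It is also fair that the sizes above are hypothetical. They require whole categories left blank while the matching aids items are recorded as No. The documents give no frequency for that pattern and do not say whether an unticked aids box is stored as No or as missing. If it is stored as No, every skipped category with no aid ticked would be affected; if it is stored as missing, a category skipped entirely would already be missing under the present text.

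**Conclusion.** The concern holds as a minor one. Applied literally, Appendix 1 gives 0 and a non-missing category when every question is blank and the indicator is No. That can understate HAQ-DI and bypass the limit of two missing categories, and it conflicts with the table column in the same appendix. The size depends on the form: under the assumed scenarios, 12.5% or 25% too low with one or two such categories, and a score where there should be none with three or more.

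A reader might go further and infer that incomplete questionnaires in this trial look healthier than they are, or that the efficacy findings are biased. The documents do not support either. Nothing shows that the pattern occurred. DAS28(CRP), the primary endpoint, does not use HAQ-DI (SAP Section 6.2.1), and neither do the secondary endpoints (Section 6.3). The study was terminated with 15 subjects enrolled and no inferential analysis is planned (Section 1.3). What is exposed is the descriptive baseline summary and any exploratory HAQ-DI summary; the exploratory methods are blacked out (Section 6.4.2), so the effect there cannot be judged.

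**What to change.** In SAP Appendix 1, under Handling Missing Data, replace the condition for a missing category with one sentence: a category score is missing when none of its questions is answered and none of its aids/device indicators is Yes. Keep the existing mean of non-missing categories and the more-than-two-missing rule, applied to categories defined this way. A category with blank questions and a reported aid still scores 2, as now.

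This brings the text into line with the table column. It also makes the result independent of whether an unticked aids box is stored as No or as missing, since both then lead to a missing category when nothing was answered.

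The cost is one sentence and one line of derivation code, with no change to data collection. The downside is that a few more HAQ-DI scores may become missing. SAP Section 1 provides for finalization of the SAP before the database is finalized, and for recording later changes in the study report, so the correction can be made at either stage.
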